Section 6.3.10 now reads: "Directed biopsies will be obtained from areas suspicious for CIN. Biopsies are taken only if lesions are seen upon colposcopy. In the event lesions are not seen upon colposcopy but the cytology specimens show presence of HSIL, then the participant should return to the study clinic for ~~endocervical curettage (ECC)~~ repeat colposcopy and other diagnostics procedure such as endocervical curettage (ECC), random cervical biopsies, or diagnostic LEEP. Results of these diagnostic tests must be recorded on the appropriate CRF. Slides from biopsies of CIN2+ and biopsies without CIN2+ will be submitted for review. If CIN2+ is detected by biopsy, the participant will undergo LEEP.

Clarification Memorandum #1 for:

A5282

A Randomized, Phase II Trial to Compare an HPV Test-and-Treat Strategy to a Cytology-based Strategy for Prevention of CIN 2+ in HIV-infected Women

A Limited Center Trial of the AIDS Clinical Trials Group (ACTG)

DAIDS ES # 10845

Clarification Memorandum Date: 5 February 2013

ACTG Network Coordinating Center

Social & Scientific Systems, Inc.
[name]
[name] 20910

[contact]
[contact]

CLARIFICATION MEMO

DATE: February 5, 2013

TO: Non-US ACTG CTU Principal Investigators, CRS Leaders, and CTU/CRS Coordinators Participating in the A5282 Study

FROM: A5282 Protocol Team

SUBJECT: Clarification Memo # 1 to the A5282 Protocol, Version 1.0, 11/16/2010, entitled "A Randomized, Phase II Trial to Compare an HPV Test-and-Treat Strategy to a Cytology-based Strategy for Prevention of CIN 2+ in HIV-infected Women"

This clarification memo does not result in a change in the protocol informed consent document. The Division of AIDS does not require you to forward it to your IRB; however, as always, you must follow your IRB's policies and procedures. If IRB review of clarification memos is required at your site, please submit this document for review.

Each site should file a copy of this clarification memo with the protocol for reference.

The protocol clarifications contained in this memo should be implemented immediately. These updates will be included in the next version of the A5282 protocol if it is amended at a future date.

The following are clarifications to A5282, Version 1.0, 11/16/2010:

1. Section 6.3.2, "Medical History" now reads:

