Cervical cytology specimens will be obtained and processed locally in real-time (refer to the A5282 MOPS). Pap smears will be interpreted locally. Results should be communicated to the participant's primary care provider, and the site must document this communication in the source documents.

Colposcopy and Directed Biopsies

At entry:

- Participants in Arm A will not have colposcopy and directed biopsies; these women will instead undergo cryotherapy.
- Participants in Arm B will undergo colposcopy with directed biopsies if the screening cytology is abnormal, i.e., the result reveals atypical squamous cells of undetermined significance (ASCUS), atypical glandular cells of undetermined significance (AGUS), low grade squamous intraepithelial lesion (LSIL), or HSIL.
- Participants in Arm C will undergo colposcopy and directed biopsies if the screening cytology shows HSIL or if cervical lesions were seen upon visual inspection.

Post entry:

- Participants in Arms A and B will undergo colposcopy and directed biopsies at the weeks 26, 78, and 130 clinic visits.
- Participants in Arm C who undergo LEEP post-entry will undergo colposcopy and directed biopsies at the week 26 clinic visit.

Digital images and colposcopic impression will be submitted for review, along with location of cervical biopsies.

Directed biopsies will be obtained from areas suspicious for CIN. Biopsies are taken only if lesions are seen upon colposcopy. In the event lesions are not seen upon colposcopy but the cytology specimens show presence of HSIL, then the participant should return to the study clinic for endocervical curettage (ECC). Slides from biopsies of CIN2+ and biopsies without CIN2+ will be submitted for review. If CIN2+ is detected by biopsy, the participant will undergo LEEP.

LEEP

Participants found to have CIN2+ by biopsy at any point during the study will be offered LEEP. If the participant had a prior LEEP, treatment of recurrent CIN2+ is at the discretion of the site investigator. These participants will continue on study. All specimens obtained by LEEP will be fixed in formalin and submitted for review. Digital images obtained immediately prior to and following LEEP will also be submitted for review.

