9.6 Analyses

9.6.1 Comparison of CIN2+ between Arms A and B

For the primary analysis, time-to-event methods will be used to estimate the cumulative rate of the primary endpoint (from week 26 to week 130 after study entry) to account for lost to follow-up. The protocol team plans to use the Turnbull estimation for the proportions of participants without CIN2+ diagnosis by the end of the study, stratified by the study stratification factors [43]. The generalized Greenwood's formula for the standard error will be used for the variance and inverse variance method to account for strata [44]. The proportions in Arms A and B will be compared using asymptotic normal distributions. A one-sided 95% upper confidence bound on the difference (Arm B proportion minus Arm A proportion) between these proportions will also be provided. A stratified log-rank test will be conducted as a secondary analysis to compare the time to development of CIN2+ between Arms A and B. The primary analysis will be conducted as intent-to-treat on all participants randomized to the study Arms A and B. In other words, participants will be included in the analyses even if cryotherapy is not performed in Arm A and participants do not adhere to the strategy in Arm B. Per-protocol analysis will also be performed on only the participants who adhere to the specified procedures in Arms A and B, as secondary analysis. Participants without complete biopsy data will be censored at their last visit with a biopsy result (i.e., weeks 26, 78, 130).

Participants in Arm B may have biopsy done prior to week 26 based on the evaluation of baseline abnormal cervical cytology, whereas participants in Arm A will not have biopsies until week 26. Participants in Arm B diagnosed prior to their week 26 visit with CIN2+ that is cleared according to the biopsy at their week 26 will not be considered failures for the primary endpoint analysis. They are counted as meeting the primary endpoint only if CIN2+ is found at week 26 or later. Unplanned biopsies in Arm A that occur prior to the week 26 visit will not be considered for the primary endpoint.

The pathologic classification for the primary endpoint will be the determination by the local review at a DAIDS-assessed laboratory. Central review will be done for quality assurance.

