### **3 Statistical Considerations**

Unless otherwise indicated, analysis will use data from all subjects who enrolled successfully to A5282 arms A and B.

For categorical measures, number of subjects and percent will be provided. For continuous measures, median, lower and upper quartiles, minimum and maximum will be provided. In data listings, participants will be identified by an anonymous patient identifier generated at the statistical center. Dates will not be shown, but will be converted to time (e.g. weeks) since randomization.

Time to CIN2+ will be computed as the number of weeks between randomization and the week 26 to week 130 biopsy week when CIN2+ was first detected. For those who did not develop CIN2+, event time will be censored at the latest among the following: time of last biopsy or last colposcopy or last pap smear. The cumulative rate of CIN2+ will be estimated using Kaplan-Meier methods. A one-sided 95% upper confidence bound on Arm B minus Arm A cumulative rates accounting for baseline ART use (i.e. [using inverse variance as weights,] weighted estimate of treatment difference across baseline ART use) will be provided.

The per-protocol secondary analysis of the primary endpoint will only include:

- a. Arm A participants who had week 0 cryotherapy, and
- b. Arm B participants with: 1) baseline NILM cytology, 2) baseline abnormal cytology (ASCUS or greater) with one or more cervical biopsies that show NILM or CIN1 as the most severe result, 3) baseline abnormal cytology (ASCUS or greater) who underwent cervical colposcopy with no lesions seen, or 4) women who had LEEP performed prior to week 16 after the week 0 CIN2+ on biopsy regardless of cytology result.

All programs that generate derived data will be validated. The calculations of time to CIN2+ and confidence interval for the primary endpoint (one-sided 95% upper confidence interval for arm B proportion minus arm A proportion) will be double-programmed.

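### SAP per-protocol item b(3) classes Arm B women with baseline HSIL and no visible lesion as adherent without the work-up in protocol 6.3.10 and, read literally, admits untreated CIN2+ found on that work-up

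*SAP*

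**What the plan says.** Protocol 9.6.1 sets the principle for the secondary analysis: "Per-protocol analysis will also be performed on only the participants who adhere to the specified procedures in Arms A and B". SAP section 3 turns this into a list. Arm A women qualify by having week 0 cryotherapy. Arm B women qualify through any of four items joined by 'or':

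- b(1): normal baseline cytology.
- b(2): abnormal cytology with biopsies whose worst result is NILM or CIN1.
- b(3): "baseline abnormal cytology (ASCUS or greater) who underwent cervical colposcopy with no lesions seen".
- b(4): LEEP before week 16 after week 0 CIN2+ on biopsy, whatever the cytology.

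Protocol 6.3.10 describes the procedures. For entry it states: "Participants in Arm B will undergo colposcopy with directed biopsies if the screening cytology is abnormal". In version 1.0 it adds: "Biopsies are taken only if lesions are seen upon colposcopy". The same subsection has a rule for HSIL cytology with no lesion at colposcopy. Version 1.0 asks for a return visit for endocervical curettage. Clarification Memo #2 (January 2014) widens this to "repeat colposcopy and other diagnostics procedure such as endocervical curettage (ECC), random cervical biopsies, or diagnostic LEEP". The Letter of Amendment that followed the March 2015 DSMB review keeps the step and adds biopsies at weeks 78 and 130 even when no lesion is seen.

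On timing, 9.6.1 notes: "Participants in Arm B may have biopsy done prior to week 26 based on the evaluation of baseline abnormal cervical cytology". Of women with CIN2+ diagnosed before week 26 and then cleared, it says: "They are counted as meeting the primary endpoint only if CIN2+ is found at week 26 or later". SAP 4.2 treats LEEP results before week 16 as baseline evaluation.

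**The concern.** A per-protocol set should match the procedures that the protocol specifies, and b(3) departs from them in two ways.

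First, 'ASCUS or greater' includes HSIL. A woman with HSIL, no visible lesion and no return work-up has missed a step in 6.3.10, yet b(3) counts her as adherent. Under the lesion-only biopsy rule at entry, that return visit was her only planned source of baseline histology.

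Second, b(3) says nothing about histology. If the return work-up finds CIN2+ and no LEEP follows before week 16, the woman fails b(4) but still meets b(3).

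Disease missed or left untreated at baseline becomes an endpoint if it is found at week 26 or later, and the random biopsies at weeks 78 and 130 can find it without a visible lesion. If these women have more events than the rest of Arm B, keeping them raises the Arm B per-protocol rate. That is the direction of the one-sided hypothesis that immediate cryotherapy is better.

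**Working it through.** **Membership check.** Apply b(1) or b(2) or b(3) or b(4) to three Arm B profiles, all with baseline HSIL and no LEEP before week 16:

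| Profile | b(1) | b(2) | b(3) | b(4) | In set? |
|---|---|---|---|---|---|
| (i) No lesion, no tissue taken | no | no | yes | no | in |
| (ii) No lesion, CIN2+ on work-up | no | no | yes | no | in |
| (iii) Lesion seen, CIN2+ on biopsy | no | no | no | no | out |

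Profiles (ii) and (iii) are both untreated CIN2+. They are classed differently only because a lesion was visible in one. Profile (i) skipped the return visit and is still in.

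**The plan's own figure.** Protocol 9.4 gives 111 per arm for 20% against 6%, one-sided 5%, 90% power. With the continuity-corrected two-proportion formula:

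- n0 = [1.645 × √(2 × 0.13 × 0.87) + 1.282 × √(0.20 × 0.80 + 0.06 × 0.94)]² / 0.14² ≈ 97.
- n = (n0/4) × [1 + √(1 + 4/(n0 × 0.14))]² ≈ 111.

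The figure is reproduced and not in dispute. It serves below only as a denominator.

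**Illustrative size.** Let k be the number of extra women whom b(3) admits and p their probability of an event from week 26 to week 130. The documents give neither, so both are assumptions. Start from 111 Arm B women at the planned 20%, which is 0.20 × 111 = 22.2 events. Then

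rate = (22.2 + k × p) / (111 + k).

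| p | k = 1 | k = 3 | k = 5 |
|---|---|---|---|
| 0.20 | 22.4/112 = 20.0% | 22.8/114 = 20.0% | 23.2/116 = 20.0% |
| 0.50 | 22.7/112 = 20.3% | 23.7/114 = 20.8% | 24.7/116 = 21.3% |
| 1.00 | 23.2/112 = 20.7% | 25.2/114 = 22.1% | 27.2/116 = 23.4% |

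The shift is 0 at p = 0.20, 0.3 to 1.3 points at p = 0.50, and 0.7 to 3.4 points at p = 1.00, the upper limit for p. Against the 14-point design difference (20% minus 6%), the largest of these is 3.45/14 = 24.6%.

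**Can k be presumed zero?** Protocol Table 1 reports HSIL or worse on cytology in 6% to 52% of women in four site cohorts. These are not the randomised population. If those rates held for 140 Arm B women and an assumed 10% to 50% of HSIL cases showed no lesion, the number with HSIL and no lesion would run from 140 × 0.06 × 0.10 = 0.8 to 140 × 0.52 × 0.50 = 36.4. Only those without the work-up, or with CIN2+ and no timely LEEP, count towards k. So k may be zero, but the documents neither show that nor cap it at five.

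**The case against.** The best defence is that b(3) matches the Arm B strategy as protocol section 3.0 summarises it: cytology, colposcopy with directed biopsies, and LEEP as needed. A woman with nothing to biopsy has followed those steps. The HSIL sentence in 6.3.10 says 'should', gives examples rather than one required test, sets no time window and is not specific to Arm B. It also follows the post-entry bullets, so it may have been written mainly for later visits, when cytology is reported after the colposcopy. This stands in part: a missed work-up departs from directive text, not from an absolute requirement. But the sentence sits in the subsection that orders the Arm B entry colposcopy and makes no exception for entry, so it remains a specified procedure under 9.6.1.

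It can also be said that the four items were meant as a partition, with any CIN2+ belonging to b(4). That is probably the intention, and the second gap does rest on a literal reading. The SAP does not say so, however, and b(4) speaks of week 0 CIN2+, which may not cover a result from a later return visit. The partition reading also leaves profile (i) untouched.

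The SAP does make these women partly visible. Section 4.1.4 lists Arm B women without LEEP after CIN2+ and those with abnormal cytology and no baseline biopsy, and section 4.2.1 plans curves by baseline cytology and histology. None of this removes anyone from the per-protocol set.

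Finally, a strict work-up condition has its own bias. It drops high-risk HSIL women from Arm B only, while HSIL women with cryotherapy stay in Arm A. That stands, and it shapes the fix.

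**Conclusion.** The concern holds as a mismatch of definition. Item b(3) does not agree with protocol 6.3.10 and 9.6.1 for HSIL without a visible lesion and, taken literally, it undoes the LEEP condition in b(4) for CIN2+ found on work-up.

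A reader might infer more, and the documents do not support it:

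- **That the trial's main result is biased.** The primary analysis is intent-to-treat on all women randomised to Arms A and B. It does not use this set, and sample size and power are unchanged. Only the secondary per-protocol analyses (CIN2+ and CIN3+) are affected.
- **That the Arm B rate is inflated by about 3 points, or a quarter of the design difference.** That figure needs five such women, all with events. Both numbers are assumed, and the true shift may be zero. A higher Arm B rate is likely only if these women have more events than the rest of Arm B. Detection without a visible lesion depends largely on the random biopsies added after March 2015.
- **That b(3) should be replaced by a strict work-up rule.** That would remove high-risk women from one arm only and could bias the comparison the other way.

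Which colposcopy b(3) means is also left unsaid. The Arm B entry colposcopy is surely intended, so that is a matter of wording.

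**What to change.** 1. **Clarify b(3) and b(4).** State that b(3) refers to the Arm B entry colposcopy and applies only if no CIN2+ was found on tissue during baseline work-up. State that any such CIN2+ is classified by b(4) only, that week 0 CIN2+ in b(4) includes CIN2+ from this work-up, and that a diagnostic LEEP before week 16 counts as the LEEP. Use the SAP's existing week 16 baseline window. A window running to the week 26 visit would clash with b(4): a woman found with CIN2+ at week 17 and treated promptly could not meet it.

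2. **Add one sensitivity per-protocol estimate.** For HSIL with no lesion seen, also require a documented tissue work-up (endocervical curettage, random biopsy or diagnostic LEEP). Report it beside the main per-protocol estimate, with the number of women who differ. Keep it as a second estimate because of the one-sided exclusion described above.

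The cost is a few SAP sentences, one additional per-protocol flag and one run. No new data are needed: the 2014 memo and the later Letter of Amendment already require the results of these diagnostic tests on the case report forms.

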### **4 Outline of Planned Analyses**

#### **4.1 Background**

##### **4.1.1 Study History**

Summary of changes and clarifications of the protocol.

#### 4.1.2 Accrual

Tables of accrual by month and site (CRS) by arm.

#### 4.1.3 Study Status

Table with:

- number of participants enrolled
- number of participants who completed study
- number of participants who discontinued the study prematurely
- follow-up time on study
- listing of participants who discontinued the study prematurely and reasons for discontinuation.
- listing of deaths and description.

#### 4.1.4 Treatment Status

Table with:

- listing of Arm A participants who did not have cryotherapy and reasons
- listing of Arm B participants who did not have LEEP after CIN2+ diagnosis
- listing of Arm B participants with abnormal cytology who do not have biopsies obtained at baseline

#### 4.1.5 Baseline Summaries

- Baseline demographics, sociodemographic and health variables: age, race/ethnicity, IV drug use history, ART use, CD4 count, nadir CD4 count, highest level of education complete, average annual household income, number of children
- Baseline sexual history: age of first vaginal sex, total number of vaginal sex partners
- Baseline cytology and Abbott hr-HPV results

**4.2 Primary Endpoint:** CIN2+ (CIN2, CIN3 or invasive cancer) by biopsy 26 weeks post randomization through 130 weeks post randomization, as determined by local review at a DAIDS-assessed laboratory

Note: LEEP outcome prior to week 16 will be considered baseline evaluation and will not be used as an endpoint.

Tables (ITT and per-protocol): cumulative rates of arm A and arm B subjects who developed CIN2+ from week 26 to week 130; one-sided 95% upper CI for arm B proportion minus arm A proportion.

SDAC validation: The calculation of time to CIN2+ and the one-sided 95% upper CI will be double-programmed.

In addition, (to evaluate design assumptions and precursory design assumptions,) the following will be reported:

- Arm A and Arm B: CIN2+ rate from week 26 to week 130
- Arm A and Arm B: week 0 invasive cancer
- Arm B: number (%) diagnosed with CIN2+ at baseline
- Arm B: number (%) with CIN2+ at baseline who were successfully treated before week 26. Note that we only have a limited number of participants with cervical (non-LEEP) biopsy results before week 26.
- number (%) of subjects with abnormal pap smear and CIN2+ at baseline
- number (%) of subjects with CIN2+ at baseline who were successfully treated before week 26.

**4.2.1 Secondary endpoint:** Time to CIN2+ diagnosis by biopsy, as determined by local review at a DAIDS-assessed laboratory

Figures (ITT and per-protocol): survival curves with p-value from stratified log-rank test comparing arms A and B.

Figure: For Arm A, survival curves with p-value from log-rank test comparing participants with and without hr-HPV at week 26 based on: (a) aHPV, and (b) Xpert

Figure: For Arm A, survival curves with p-value from log-rank test comparing participants with and without cervical cytologic abnormalities at week 26.

Figures (ITT): survival curves with p-value from stratified log-rank test comparing arms A and B.

Figures (ITT): survival curves with p-value from stratified log-rank test comparing arms A and B for those with: (a) CIN2+ on histology at baseline, (b) CIN1 on histology at baseline, (c) NILM cytology result at baseline, (d) ASCUS/LSIL cytology result at baseline and (e) HSIL/ASC-H cytology result at baseline.

**4.2.2 Secondary endpoint:** CIN3+ (CIN3 or invasive cancer) by biopsy 26 weeks post randomization through 130 weeks post randomization, as determined by local review at a DAIDS-assessed laboratory.

NOTE: Time to CIN3+ will be computed as the number of weeks between randomization and the biopsy week when CIN3+ was detected. For those who did not develop CIN3+, event time will be censored at the latest among the following: time of last biopsy or last colposcopy or last pap smear.

Tables (ITT and per-protocol): cumulative rates of arm A and arm B subjects who developed CIN3+ from week 26 to week 130; two-sided 95% CI for arm B proportion minus arm A proportion.

Figures: survival curves with p-value from stratified log-rank test comparing arms A and B

